Attachment 6: Revised Response Criteria for Response Assessment¹²

Response and Site	PET-CT–Based Response	CT-Based Response
Complete	Complete metabolic response	Complete radiologic response (all of the following)
Lymph nodes and extralymphatic sites	Score 1, 2, or 3* with or without a residual mass on 5PS† It is recognized that in Waldeyer’s ring or extranodal sites with high physiologic uptake or with activation within spleen or marrow (eg, with chemotherapy or myeloid colony-stimulating factors), uptake may be greater than normal mediastinum and/or liver. In this circumstance, complete metabolic response may be inferred if uptake at sites of initial involvement is no greater than surrounding normal tissue even if the tissue has high physiologic uptake	Target nodes/nodal masses must regress to ≤ 1.5 cm in LDi; No extralymphatic sites of disease
Nonmeasured lesions	Not applicable	Absent
Organ enlargement	Not applicable	Regress to normal
New lesions	None	None
Bone marrow	No evidence of FDG-avid disease in marrow	Normal by morphology; if indeterminate, IHC negative
Partial	Partial metabolic response	Partial remission (all of the following)
Lymph nodes and extralymphatic sites	Score 4 or 5† with reduced uptake compared with baseline and residual mass(es) of any size	$\geq 50\%$ decrease in SPD of up to 6 target measurable nodes and extranodal sites from baseline; When a lesion is too small to measure on CT, assign 5mm×5mm as the default value; When no longer visible, 0×0mm; For a node > 5mm× 5mm, but smaller than normal, use actual measurement for calculation
Nonmeasured lesions	Not applicable	Absent/normal, regressed, but no increase
Organ enlargement	Not applicable	Spleen must have regressed by >50% in length beyond normal
New lesions	None	None
Bone marrow	Residual uptake higher than uptake in normal marrow but reduced compared with baseline (diffuse uptake compatible with reactive changes from chemotherapy allowed). If there are persistent focal changes in the marrow in the context of a nodal response, consideration should be given to further evaluation with MRI or biopsy or an interval scan	Not applicable
No response or stable disease	No metabolic response	Stable disease
Target nodes/nodal masses, extranodal lesions	Score 4 or 5 with no significant change in FDG uptake from baseline	<50% decrease from baseline in SPD of up to 6 dominant, measurable nodes and extranodal sites; no criteria for progressive disease are met

Response and Site	PET-CT–Based Response	CT-Based Response
Nonmeasured lesions	Not applicable	No increase consistent with progression
Organ enlargement	Not applicable	No increase consistent with progression
New lesions	None	None
Bone marrow	No change from baseline	Not applicable
Progressive disease	Progressive metabolic response	Progressive disease requires at least 1 of the following
Target nodes/nodal masses, extranodal lesions	Score 4 or 5 with an increase in intensity of uptake from virtually determined nadir	PPD progression: An individual target (nodal or extranodal) must be abnormal with: Node >1.5 cm in LDi or extranodal lesion >1.0 cm in any axis; Increase by $\geq 50\%$ from PPD nadir and An increase in LDi or SDi from nadir: ≥ 0.5 cm for lesions ≤ 2 cm ≥ 1.0 cm for lesions > 2 cm In the setting of splenomegaly, the splenic length must increase by $> 50\%$ of the extent of its prior increase beyond baseline (eg, a 15-cm spleen must increase to > 16 cm). If no prior splenomegaly, must increase by at least 2 cm from baseline New or recurrent splenomegaly
Nonmeasured lesions	None	New or clear progression of preexisting nonmeasured lesions
New lesions	New FDG-avid foci consistent with lymphoma rather than another etiology (eg, infection, inflammation). If uncertain regarding etiology of new lesions, biopsy or interval scan may be considered.	Regrowth of previously resolved lesions A new node > 1.5 cm in LDi; A new extranodal site > 1.0 cm in any axis; if < 1.0 cm in any axis, its presence must be unequivocal and must be attributable to lymphoma; Assessable disease of any size unequivocally attributable to lymphoma
Bone marrow	New or recurrent FDG-avid foci	New or recurrent involvement

Response and Site	PET-CT–Based Response	CT-Based Response

Abbreviations: 5PS, 5-point scale; CT, computed tomography; FDG, fluorodeoxyglucose; IHC, immunohistochemistry; LDi, longest transverse diameter of a lesion; MRI, magnetic resonance imaging; PET, positron emission tomography; PPD, cross product of the LDi and perpendicular diameter; SDi, short diameter, the widest part of the lesion perpendicular to the LDi; SPD, sum of the product of the perpendicular diameters for multiple lesions.
 
*A score of 3 in many patients indicates a good prognosis with standard treatment, especially if at the time of an interim scan. However, in trials involving PET where de-escalation is investigated, it may be preferable to consider a score of 3 as inadequate response (to avoid undertreatment). Measured dominant lesions: Up to six of the largest dominant nodes, nodal masses, and extranodal lesions selected to be clearly measurable in two diameters. Nodes should preferably be from disparate regions of the body and should include, where applicable, mediastinal and retroperitoneal areas. Non-nodal lesions include those in solid organs (eg, liver, spleen, kidneys, lungs), GI involvement, cutaneous lesions, or those noted on palpation. Nonmeasured lesions: Any disease not selected as measured, dominant disease and truly assessable disease should be considered not measured. These sites include any nodes, nodal masses, and extranodal sites not selected as dominant or measurable or that do not meet the requirements for measurability but are still considered abnormal, as well as truly assessable disease, which is any site of suspected disease that would be difficult to follow quantitatively with measurement, including pleural effusions, ascites, bone lesions, leptomeningeal disease, abdominal masses, and other lesions that cannot be confirmed and followed by imaging. In Waldeyer’s ring or in extranodal sites (eg, GI tract, liver, bone marrow), FDG uptake may be greater than in the mediastinum with complete metabolic response, but should be no higher than surrounding normal physiologic uptake (eg, with marrow activation as a result of chemotherapy or myeloid growth factors).
 
†PET 5PS: 1, no uptake above background; 2, uptake\leqmediastinum; 3, uptake$>$mediastinum but\leqliver; 4, uptake moderately$>$ liver; 5, uptake markedly higher than liver and/or new lesions; X, new areas of uptake unlikely to be related to lymphoma.
		

INVESTIGATOR AGREEMENT

JNJ-54767414 Daratumumab

1. INTRODUCTION

This statistical analysis plan (SAP) contains definitions of analysis sets, derived variables, and statistical methods for all planned analysis.

1.1. Trial Objectives

Primary Objectives

The primary objective of the study is to evaluate the efficacy of daratumumab in subjects with NKTCL by ORR including complete response (CR) and partial response (PR) based on a blinded independent central review (BICR) per Revised Criteria for Response Assessment of Hodgkin and non-Hodgkin Lymphoma: LUGANO classification.

Secondary Objectives

- To evaluate the efficacy of daratumumab in NKTCL by CR rate, progression free survival (PFS), duration of response (DoR), time to response based on a BICR, and OS
- To evaluate safety and tolerability
- To evaluate PK and immunogenicity

1.2. Trial Design

This is an open-label, single arm, multicenter, phase 2 study to evaluate the efficacy and safety of daratumumab monotherapy in subjects with relapsed and refractory extranodal NKTCL, nasal type. Each cycle will consist of 28 days.

The study is designed as Simon's 2-stage with an interim analysis conducted after approximately 15 subjects who have received at least one dose of study drug and had at least one post-baseline disease evaluation. The purpose of the interim analysis is to evaluate efficacy and safety data in stage 1 and facilitate the early preparation for the next step of development. The totality of efficacy (ORR), safety, and biomarker data will be analyzed at the interim. Enrollment may be put on hold pending the decision of interim analysis unless the decision is clear based on available data before IA. The study may be terminated if the futility criteria are met and supported by totality of data. In addition, at interim, the association between daratumumab activity and CD38 expression level will be explored. A population enrichment strategy may be applied after the interim analysis if such a strategy is supported by emerging data. If the study proceeds to the second stage, the total sample size will be 32 with 2 stages combined. Following that, additional patients (ie, up to 35 patients) may be enrolled in an expansion phase to confirm the clinical response rate of daratumumab, if supported by emerging data.

1.3. Statistical Hypotheses for Trial Objectives

It is hypothesized that treatment with daratumumab results in an ORR of >30% versus a null hypothesis of at most 15% in relapsed or refractory NKTCL, nasal type subjects who failed (relapsed or refractory after achieving complete or partial remission) at least one line of chemotherapy.

1.4. Sample Size Justification

The study is designed to evaluate the effect of daratumumab on ORR utilizing Simon's 2-stage design. The null hypothesis is that ORR is at most 15%, and the alternative hypothesis is that ORR is at least 30%. With a 1-sided alpha of 10%, and a power of 78%, a total of 32 subjects are to be enrolled into the study. The stage 1 analysis is to be performed when approximately 15 subjects are enrolled in the study and have sufficient data for response evaluation. The futility criterion of ORR is defined as when at most 1 out of 15 subjects have achieved CR/ PR after stage 1 according to Simon's 2-stage design. Future enrollment into stage 2 may be terminated if it is determined during the first stage that the treatment group is considered as ineffective or not well tolerated. If study proceeds to second stage with a total of 32 subjects with 2 stages combined, the null hypothesis is to be rejected if 8 or more responders are observed.

To achieve 1-sided alpha of 2.5% and a power of 80%, additional patients (ie, up to 35 patients) may be enrolled in an expansion phase to confirm the clinical response rate of daratumumab if supported by emerging data.

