10.2. Sample Size Determination

The study is designed to evaluate the effect of daratumumab on ORR utilizing Simon's 2-stage design. The null hypothesis is that ORR is at most 15%, and the alternative hypothesis is that ORR is at least 30%. With a 1-sided α of 10%, and a power of 78%, a total of 32 subjects are to be enrolled into the study. The stage 1 analysis is to be performed when approximately 15 subjects are enrolled in the study and have sufficient data for response evaluation. The futility criterion of ORR is defined as when at most 1 out of 15 subjects have achieved CR/PR after stage 1 according to Simon's 2-stage design. Future enrollment into stage 2 may be terminated if it is determined during the first stage that the treatment group is considered as ineffective or not well-tolerated. If study proceeds to second stage with a total of 32 subjects with 2 stages combined, the null hypothesis is to be rejected if 8 or more responses are observed.

To achieve 1-sided α of 2.5% and a power of 80%, additional patients (ie, approximately 35 patients) may be enrolled in an expansion phase to confirm the clinical response rate of daratumumab if supported by emerging data.

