2. GENERAL ANALYSIS DEFINITIONS

Unless specifically stated, the summary will be analyzed and presented by total subjects combined.

The analyses for continuous variables will be summarized by descriptive statistics (mean, standard deviation, median, and range). Categorical variables will be presented with frequency, percentage, or 95% CI if appropriate. Time to event variables will be summarized by descriptive Kaplan-Meier statistics, or 95% CI if appropriate.

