2.8. Analysis Sets

2.8.1. Efficacy Analysis Set(s)

The all treated analysis set will consist of all subjects who receive at least 1 dose of daratumumab. This analysis set will be used for efficacy analysis unless otherwise stated.

The response evaluable analysis set will consist of all subjects who satisfy all of the following:

- Received at least 1 dose of study drug;
- Had a baseline and at least 1 post-treatment disease evaluation.

Response evaluable analysis set will be used for the efficacy analyses at interim analysis.

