5. EFFICACY

5.1. Analysis Specifications

The analysis of efficacy will be based on BICR for all treated population. Sensitivity analysis will be performed based on investigators' assessment.

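### Does the 80% power stated for the expansion fail if the expansion opens only after a positive 32-subject result?

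*SAP*

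**What the plan says.** SAP 1.4 describes a Simon two-stage design with a null ORR of at most 15% and an alternative of at least 30%. The futility boundary is 1 or fewer responders in 15, and SAP 3 makes it non-binding. For the two stages together, "With a 1-sided alpha of 10%, and a power of 78%, a total of 32 subjects are to be enrolled into the study", and "the null hypothesis is to be rejected if 8 or more responders are observed".

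A further step follows: "To achieve 1-sided alpha of 2.5% and a power of 80%, additional patients (ie, up to 35 patients) may be enrolled". SAP 1.2 gives the condition: the extra patients "may be enrolled in an expansion phase to confirm the clinical response rate of daratumumab, if supported by emerging data". Protocol 10.2 has the same step with slightly different wording on size: "additional patients (ie, approximately 35 patients) may be enrolled in an expansion phase to confirm the clinical response rate".

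No responder count is given for opening the expansion and no cut-off for the enlarged sample. SAP 5.1.1 sets no significance level. The analysis population is pooled by default. Under SAP 2, "the summary will be analyzed and presented by total subjects combined". SAP 2.8.1 says of the all treated set, "This analysis set will be used for efficacy analysis unless otherwise stated", and SAP 5.1 adds "The analysis of efficacy will be based on BICR for all treated population". SAP 5.2.2 plans a two-sided 95% exact interval for ORR.

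**The concern.** The two power figures seem to conflict. An expansion meant to confirm a response rate is most naturally read as following a positive result, and the only success rule stated at 32 subjects is 8 or more responders. Under that reading every trial that succeeds at the end must first pass a test whose own power is 78%. Overall power then cannot reach 80%, however many patients are added. A drug with a true ORR of 30% would be missed in about 28% of trials rather than 20%. To keep 80%, the expansion would have to open at 6 or 7 of 32, where the plan's own test has not rejected the null.

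A second worry is size. The SAP's upper limit of 35 would allow a smaller expansion, and some smaller sizes miss 80% even with no condition at 32. Since 80% power is the stated reason for enrolling these patients, the figure deserves a check.

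**Working it through.** **Inputs.** Null ORR 15%, alternative 30%, looks at 15 and 32 subjects, futility at 1/15 or fewer, rejection at 8/32 or more, and 35 added subjects (32 + 35 = 67), all from SAP 1.4. The boundary is non-binding (SAP 3), so results are shown with futility followed, then overridden. All calculations are exact binomial.

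**1. The 32-subject figures.** P(at least 2/15 and at least 8/32) is 0.0938 at 15% and 0.7809 at 30%. The plan's 10% and 78% reproduce. With futility overridden, power is 0.7882.

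**2. What the 80% refers to.** The 35 new subjects alone cannot supply it. The smallest count with a null tail of at most 2.5% is 11/35 (tail 0.0110), with power 0.490. For the pooled 67 the cut-off is 17:

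- P(X ≥ 16 | 67, 0.15) = 0.0369, too large
- P(X ≥ 17 | 67, 0.15) = 0.0183, acceptable

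The planned exact interval gives the same cut-off: its lower limit is 14.3% at 16/67 and 15.5% at 17/67. Power is P(X ≥ 17 | 67, 0.30) = 0.8311, or 0.8139 with futility followed. The stated 80% is the pooled figure and is correct.

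**3. Effect of an opening rule.** Suppose the expansion opens only at g or more responders in 32. Overall power is the sum over x ≥ g of P(X32 = x) × P(Y35 ≥ 17 − x), at ORR 30%:

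| Lowest count that opens | Futility followed | Futility overridden |
|---|---|---|
| any | 81.4% | 83.1% |
| 6/32 | 80.3% | 81.6% |
| 7/32 | 77.6% | 78.6% |
| 8/32 | 71.7% | 72.3% |

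With 8/32 required and a larger expansion, futility followed, power is 74.2% for 50 added, 77.6% for 100 and 78.1% for 1,000. The ceiling is step 1's figure: 78.1%, or 78.8% overridden. Given 8/32 or more, the chance of reaching 17/67 is 0.7170 / 0.7809 = 91.8%, so 80% is not a conditional figure either.

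**4. Sensitivity to the cut-off.** The 72% depends on 17/67. Requiring 8/32 first leaves the 17/67 test with type I error of only 1.26% to 1.28%. A cut-off of 16/67 would then have 2.2% to 2.3%, still within 2.5%, and power of 74.9% or 75.5%.

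**5. Type I error at 17/67.** With no opening rule it is 1.75% (followed) or 1.83% (overridden); at 6/32, 1.68% or 1.74%; at 8/32, 1.26% or 1.28%. An opening rule can only lower it.

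**6. Expansion size, no opening rule.** Because counts are whole numbers, power moves in a saw-tooth (followed / overridden):

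| Added | Cut-off | Power |
|---|---|---|
| 29 | 16/61 | 76.7% / 78.1% |
| 30 | 16/62 | 78.9% / 80.4% |
| 31 | 16/63 | 80.8% / 82.5% |
| 32 | 16/64 | 82.6% / 84.4% |
| 33 | 17/65 | 77.5% / 79.0% |
| 34 | 17/66 | 79.5% / 81.1% |
| 35 | 17/67 | 81.4% / 83.1% |

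**The case for a change.** The strongest case for a change is that the plan makes the expansion conditional while quoting a power that assumes almost no condition. That does not require the exact 8/32 rule, since a rule of 7/32 already falls below 80%. The 78% ceiling under an 8/32 rule does not depend on the inferred cut-off. A sponsor who opens the expansion at 6 or 7 of 32 does so after its own test has failed, and it would be candid to say so. A few sentences written before the decision would settle it.

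The arithmetic stands, and so does the observation that the opening rule is unwritten. The step from there to a required change does not. The 8/32 condition is a reading, not something either document states. The only formal interim look is at about 15 subjects, and decisions there draw on response, safety and biomarker data together. A fixed responder count for the expansion would trade that flexibility for a firmer power figure, a matter of preference in a single-arm phase 2 study.

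The obvious repairs also gain little. A minimum of 6/32 keeps 80.3% only if the expansion always opens at 6/32. Results of exactly 6/32 contribute 80.3 − 77.6 = 2.7 points, and the margin is 0.3 points, so declining slightly more than one in ten of those cases loses it. That rule would also open the expansion in 32.0% of trials at the null rate, against 9.4% under 8/32, or (0.3200 − 0.0938) × 35 = about 8 more patients on average. Printing 72% would rest on a cut-off the plan does not state. Writing 17/67 into SAP 5.1.1 repeats what the planned exact interval implies, and the number would not carry over if the primary analysis moved to a CD38-enriched population, as Protocol 10.9 and SAP 3 allow.

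**Conclusion.** The concern does not call for a change. The stated 80% is right for the pooled 67-subject test when nothing is required at 32 (81.4% to 83.1%), or when the expansion always opens at 6/32 or more (80.3% to 81.6%). It would be too high under a stricter rule: 77.6% to 78.6% at 7/32, and about 72% at 8/32 (about 75% with the 16/67 cut-off). The documents impose neither.

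Power here is a planning figure. The ORR estimate and exact interval on all treated subjects are computed the same way whatever was planned, and type I error stays at or below 1.83%. The gap is an unstated opening rule, a fair trade-off against judging all the data. An analyst can read the cut-off off the exact interval. The difference between the two documents on expansion size is a wording slip; at 35, the number both name, the power holds.

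This rests on looks at exactly 15 and 32 subjects, full enrolment of the 35 once the expansion opens, no enrichment, and the 17/67 cut-off inferred from the exact interval.

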1.5. Randomization and Blinding

Not applicable.

2. GENERAL ANALYSIS DEFINITIONS

Unless specifically stated, the summary will be analyzed and presented by total subjects combined.

The analyses for continuous variables will be summarized by descriptive statistics (mean, standard deviation, median, and range). Categorical variables will be presented with frequency, percentage, or 95% CI if appropriate. Time to event variables will be summarized by descriptive Kaplan-Meier statistics, or 95% CI if appropriate.

2.1. Visit Windows

Any analysis that uses time-to-event data will be based on the exact determination of time from first dose of Dara to the date of the event. For the calculation of time-to-event and duration-of-event variables, the difference between the start date and the end date plus 1 day will be used.

For analyses of data by cycle, if data are collected by date (ie, AE onset), the corresponding study evaluations will be assigned to actual sequential cycles, which are derived from the study treatment administration data. The start date of a particular cycle is defined as the date of the first Dara, and the end date of a cycle is the start date of the next cycle minus 1. For the last cycle, the end date is defined as the end of treatment visit date or the minimum of last study treatment date plus 30 days or subsequent anticancer therapy minus 1 day, if the end of treatment visit date is not available.

In general, if data (e.g., laboratory and vital sign, etc.) are collected by cycle, the nominal cycle will be used to summarize data.

2.2. Pooling Algorithm for Analysis Centers

All data will be pooled together regardless of analysis centers.

2.3. Study Treatment and Study Drug

In this study, Study treatment/Study drug refers daratumumab.

2.4. Study Treatment Dosing Date

Study treatment dosing date is the date on which a subject actually received study treatment (partial or complete) and will be recorded in the study treatment administration dataset. The first study treatment date is defined as the earliest date of non-zero dose of daratumumab. The last study treatment date is defined as the latest date of non-zero dose of the daratumumab.

2.5. Treatment Cycle

A subject is considered as treated in a cycle if he/she receives any non-zero dose of daratumumab in that cycle.

2.6. Baseline Measurement

Baseline measurement is defined as the closest non-missing measurement taken on or prior to the date of first study agent administration (including time if available). If the first study treatment date is missing, the corresponding visit date should be used.

2.7. Imputation of Partial Dates

Unless specified otherwise, no data imputation will be applied for missing safety and efficacy evaluations. For analysis and reporting purpose, missing or partial dates in adverse event (AE onset date; AE end date), concomitant therapies (start date; end date), prior therapy (start date; end date), initial disease diagnosis date and start date of subsequent anticancer therapy will be imputed.

2.7.1. Missing/Partial Adverse Event Onset Date

If the onset date of an adverse event is missing partially, the following imputation rules will be used.

- When month and year are present and the day is missing,
 - If the onset month and year are the same as the month and year of first study treatment, the day of first study treatment or the day-component of the AE end date (possibly imputed) is imputed, whichever is earlier
 - If the onset month and year are not the same as the month and year of first study treatment, then the first day of the month is imputed
- When only a year is present or no components of the onset date are present,
 - If the onset year is the same as the year of first study treatment. If AE end date is available and is prior to first study treatment, the day and month of AE end date are imputed. Otherwise, the day and month of first study treatment are imputed
 - If the onset year is different from the year of first study treatment, the 1st of January is imputed
- If the onset date is completely missing, the date of first study treatment is imputed as the onset date.

No imputation will be done for partial or missing AE onset time.

If AE onset date needs imputation, but the AE onset time is available, the AE onset time will be dropped in the imputed AE onset date/time variable.

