2.7.2. Missing/Partial Adverse Event End Date

If the end date of an adverse event is missing partially, the following imputation rules will be used.

- If month and year are present and the day of the month is missing, the last day of the month is imputed.
- If only a year is present, the 31st of December is used.
- If the imputed date is later than the date of death (if available), the date of death will be used as the imputed date instead.

No imputation will be done for partial or missing AE end time.

If AE end date needs imputation, but the AE end time is available, the AE end time will be dropped in the imputed AE end date/time variable.

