2.7.3. Partial Concomitant Medication Start/End Date

In case of partially missing concomitant medication start/end dates, the following imputation rules will be applied. If the date is completely missing, no imputation will be performed.

- If only the day is missing, the 15th day of the month will be used
- If both the day and month are missing, the 30th of June will be used

If the medication was taken prior to study start, and the imputed start date is after first treatment date, further adjust the imputed start date as the day prior to first dosing date; if the medication was taken after study start, and the imputed start date is prior to first dosing date, further adjust the imputed start date as first dosing date.

After applying above adjusting method, if it results in medication start date that is after medication end date, the medication start date needs re-adjustment as follows:

If medication start date was imputed then adjust as follows:

- Impute the same month and year as medication end date if the non-imputed date parts are the same
- Impute the first day of the month as medication start day

If medication end date was imputed then re-adjust medication end date to be the same as the medication start date if the corresponding non-imputed date parts match the medication start date.

Also adjust the imputed medication end date so that it is on or after first dosing date.

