6. SAFETY

Unless specifically stated, the observations that occurred during treatment period (i.e., within 30 days from the last study drug dosing) will be used for safety analyses. All observations will be presented in listings.

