6.1. Adverse Events

The verbatim terms used in the CRF by investigators to identify adverse events will be coded using the most current version of the Medical Dictionary for Regulatory Activities (MedDRA). Toxicities will be graded for severity according to CTCAE, Version 4.03. All reported adverse events with onset during the treatment period (ie, treatment-emergent adverse events, and adverse events that have worsened since baseline, and within 30 days from the last dose) will be included in the analysis and reported using descriptive statistics and frequency tabulations.

The incidence of TEAEs will be summarized overall, by MedDRA system organ class (SOC) and preferred term, by toxicity grade, and by relationship to study treatment administration.

Specifically, the following will be summarized or listed:

- All adverse events
- Grade 3 or higher adverse events
- Serious adverse events
- Adverse events leading to discontinuation of treatment
- Treatment-emergent infusion related reactions
- Adverse events leading to treatment cycle delays or dose modifications
- Adverse events leading to death

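### When only the AE onset day is missing, SAP 2.7.1 as worded can date an AE that began in the first-dose month and ended in a later month before treatment, removing it from the treatment-emergent summaries

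*SAP*

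**What the plan says.** SAP 2.7.1 has a branch for AEs with month and year of onset known and only the day missing. Its trigger is: "If the onset month and year are the same as the month and year of first study treatment". The instruction is then that "the day of first study treatment or the day-component of the AE end date (possibly imputed) is imputed, whichever is earlier". Nothing in the branch asks whether the AE ended in that month.

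Four other places bear on the result:

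- **SAP 2.7.1, year-only branch:** "If AE end date is available and is prior to first study treatment, the day and month of AE end date are imputed". This compares the complete end date with first treatment.
- **SAP 2.7.2, end day missing:** "If month and year are present and the day of the month is missing, the last day of the month is imputed". An imputed end date later than death is reset to the date of death.
- **SAP 2.7.3, concomitant medication:** if a drug was taken after study start but its imputed start falls before first dose, the instruction is to "further adjust the imputed start date as first dosing date". There is no counterpart for AEs.
- **SAP 6 and 6.1:** the AE tables take "All reported adverse events with onset during the treatment period", and the parenthesis that follows adds "adverse events that have worsened since baseline, and within 30 days from the last dose". For all data, "All observations will be presented in listings".

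**The concern.** The first-dose branch names the day number of the end date, not the end date itself. Day numbers can be ordered sensibly only within one month. If the AE runs into the next month, a small end-day number says nothing about whether the AE began before first dose, yet the rule turns it into a pre-dose onset.

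At stake are the treatment-emergent counts in SAP 6.1, including the Grade 3 or higher, serious and related-event summaries. A misdated record would not look wrong: Protocol 11.3.1 collects AEs from consent, and Protocol 3.1 allows up to 21 days of screening, so a pre-dose onset is plausible on its face.

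The result also sits oddly beside the rest of SAP 2.7.1. When the onset date is wholly missing, the SAP imputes the first-dose date, so the event counts. Knowing the onset month can therefore give a less conservative answer than knowing nothing.

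**Working it through.** The plan states no figure on this point, so there is none to reproduce. The check applies the rule as worded and compares it with a full-date rule.

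**Formulas** (onset day missing, onset month = first-dose month)

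- As worded: imputed day = min(day of first dose, day of AE end), placed in the onset month.
- Full-date rule: imputed date = min(first-dose date, AE end date).

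**Worked cases, first dose 20 March, onset recorded as March**

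| AE end | As worded | Full-date rule |
|---|---|---|
| 10 March | min(20, 10) = 10 March, pre-dose | 10 March, pre-dose |
| 28 March | min(20, 28) = 20 March | 20 March |
| 5 April | min(20, 5) = 5 March, pre-dose | 20 March |
| 25 April | min(20, 25) = 20 March | 20 March |
| 30 April | min(20, 30) = 20 March | 20 March |

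The rules differ only where the AE ends in a later month on a smaller day number than first dose.

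**Direction.** As worded, the imputed day can never exceed the first-dose day. Where the rules differ, the literal rule gives a pre-dose date and the full-date rule gives the first-dose date. So the difference can only remove treatment-emergent events.

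**Partly missing end dates.** SAP 2.7.2 usually sets a missing end day to 28–31, which mostly protects against the fault. One exception is the reset to death: first dose 20 March, onset March, end unknown day in April, death 5 April. The end becomes 30 April, is reset to 5 April, and the onset becomes 5 March.

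**Frequency under assumed durations.** Every first-dose day of a 365-day year was taken with equal weight, with true onset equally likely on any day from first dose to month end. All these AEs are truly on treatment. The durations and the uniform onset are assumptions, not figures from the documents.

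| AE duration (days) | Runs into a later month | Dated pre-dose, as worded | Pre-dose share of those crossing |
|---|---|---|---|
| 1 | 0% | 0% | – |
| 3 | 23.1% | 22.7% | 98.6% |
| 7 | 50.5% | 48.1% | 95.2% |
| 14 | 78.1% | 66.6% | 85.3% |
| 21 | 92.7% | 62.6% | 67.5% |
| 30 | 99.8% | 18.4% | 18.4% |
| 60 | 100% | 20.3% | 20.3% |
| 90 | 100% | 23.9% | 23.9% |

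Every misdated case ended in a later month. The full-date rule dated none of these AEs before first dose, at any duration.

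**Simpler assumption.** Let first-dose day x and end day be independent and uniform on 1–30, for an AE that ends in a later month. The share misdated is the mean of (x − 1)/30 over x = 1 to 30, that is (0 + 1 + … + 29)/900 = 435/900 = 48.3%. This is a share of month-crossing AEs; the 48.1% for 7-day AEs in the table has a different denominator.

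**The case against.** The best defence is that the rule is meant chronologically. Only the day is missing in this branch, so the day-component may simply describe what fills the gap once two full dates have been compared. If onset is in the first-dose month and the AE ended before first dose, the end must lie in that month too, and inserting its day number gives exactly the right date. The year-only branch makes the full-date comparison openly. A programmer who reads it this way produces no error. That reading is possible and probably intended, but the sentence does not say so, and two programmers could derive different counts from it.

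Three stronger inferences are tempting, and the documents do not support them.

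- **That such events vanish from all reporting.** SAP 6.1 also admits AEs that worsened since baseline, SAP 6 keeps everything in listings, and SAP 6.2.1 summarises deaths without any AE-onset condition.
- **That first-infusion toxicity is what gets lost.** An AE that ends within the first-dose month is unaffected, which covers same-day infusion reactions. Those are also unlikely to lack an onset day, since they occur at a dated infusion and Protocol 8.3.4 asks for a blood sample. Weekly visits in Cycles 1–2, 24-hour SAE reporting (Protocol 11.3.2) and source checks (Protocol 16.8) should keep partial dates few.
- **That 48% measures the impact.** It rests on uniform, independent days, and its denominator is unknown.

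Some AEs with a matching onset month did begin during screening. If such an AE crosses a month end, the full-date rule would count it as treatment-emergent. That errs on the cautious side, as the SAP already does for a wholly missing onset.

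**Conclusion.** The rule is wrong as worded. Taken literally, it gives a pre-dose onset to an AE with a missing onset day in the first-dose month that ends in a later month on a smaller day number. Nothing else in the SAP corrects this. The event then drops out of the treatment-emergent summaries unless it is recorded as worsened since baseline.

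The direction is certain relative to a full-date rule: treatment-emergent events can only be lost. The size is not known, because the documents give no count of partial onset dates, and it may be small. Given such a record for a truly on-treatment AE, the chance of a pre-dose date runs from 0% to about 67% across the durations tried. Among month-crossing AEs it runs from about 18% to 99%, or 48% under the uniform assumption. With 32 planned subjects, losing one subject's only occurrence of an event moves its incidence by 1/32 = 3.1 percentage points.

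The primary endpoint and the Simon decision rule are untouched. This is a precise, nearly free correction to a safety derivation, and worth making on that ground.

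**What to change.** Reword the first-dose-month branch of SAP 2.7.1 along these lines: impute the first study treatment date, unless the complete AE end date (imputed under SAP 2.7.2 if need be) falls before first study treatment; in that case impute the AE end date. This matches the full-date comparison in the year-only branch and still dates an AE that ended before first dose correctly.

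SAP 2.7.5 uses the same day-component wording for the start of subsequent anticancer therapy and should be aligned in the same edit.

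The cost is one SAP sentence and one line of code for the AE rule, plus the parallel edit in 2.7.5. No data collection changes.
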